## 11.2 Trial analysis sets

All screened subjects will be accounted for in the CTR.

All subjects randomized will be included in the FAS and will be analyzed for efficacy based on the planned (randomized) treatment allocation. Exclusions from the FAS can be considered in special cases as described in ICH E9, Section 5.2.1., Full Analysis Set. If it is decided to exclude a randomized subject from the FAS, a justification addressing ICH E9 will be given.

A safety analysis set will be defined as all subjects who received IMP and will be analyzed according to the actual treatment received.

A PK analysis set will be defined as all subjects who received at least 1 dose of LEO 138559 and have at least 1 quantifiable PK sample.

The decisions regarding inclusion/exclusion of subjects or subject data from the trial analysis sets will be documented in the analysis set definition document before breaking the randomization code.

## 11.3 Statistical analysis

### 11.3.1 General principles

Baseline measurements are defined as the latest available observation at or prior to the date of the first IMP administration, unless otherwise specified.

All significance tests will be two-sided using the 5% significance level. All CIs will be presented with 95% degree of confidence, unless otherwise specified. LSmeans will be estimated using the observed margins for the FAS.

THIS DOCUMENT CONTAINS CONFIDENTIAL INFORMATION AND MUST NOT BE COPIED OR MADE AVAILABLE TO ANY THIRD PARTY WITHOUT THE PRIOR WRITTEN CONSENT OF THE LEO PHARMA GROUP

An observed-cases approach will be used for tabulations of data by visit (that is, involving only those subjects who attended each specific visit).

Categorical data will be summarized using the number and percentage of subjects in each category and treatment group. Continuous data will be summarized using the mean, SD, median, 1st quartile and 3rd quartile, minimum, and maximum values.

All the analyses specified in the protocol will be reviewed in relation to the blinded data actually obtained, and the SAP will be finalized before breaking the randomization code.

Any changes from the statistical analyses planned in this clinical trial protocol will be described and justified in a protocol amendment, the SAP and/or in the CTR, dependent on the type of change.

Unless otherwise stated, efficacy analyses will be performed based on the FAS, safety analyses will be based on the safety analysis set, and PK analyses will be based on the PK analysis set.

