- k) In order to ensure a sufficient number of subjects naive for biologics and systemic JAK inhibitors used for their AD, there will be a capping at 50% of subjects who received prior treatment with such therapies. These capping criteria will also apply for Japanese subjects.
- l) Nocturnal [REDACTED], Difficulty [REDACTED], and Frequency of [REDACTED] During the Night (to be completed in the morning), and ADSD (to be completed in the evening) will be initiated at least 7 days prior to baseline (Day 1) and will be completed in the eDiary daily. After Week 16, only ADSD will be completed. Subjects who discontinue IMP, but remain in the trial, will continue completing the eDiary until the Week 16 visit.
- m) PGI-S includes: [REDACTED], ADSD, Nocturnal [REDACTED], Difficulty [REDACTED], and Frequency of [REDACTED] During the Night.
- n) PGI-C includes: [REDACTED], ADSD, Nocturnal [REDACTED], Difficulty [REDACTED], and Frequency of [REDACTED] During the Night.
- o) Vital signs must be assessed prior to IMP administration. In addition, at Weeks 0, 1, 2, 3, and 4, subjects will be monitored after IMP administration for potential immediate drug reactions for a minimum of 2 hours with vital signs taken immediately (within 5 minutes) after last IMP administration as well as after 30 minutes ( $\pm$  5 minutes), after 1 hour ( $\pm$  5 minutes), and after 2 hours ( $\pm$  5 minutes), or until stable, whichever is later.
- p) Samples to be collected pre-dose.
- q) Skin tape strips will be collected at selected trial sites.
- r) Skin biopsies will be collected at selected trial sites. It is voluntary for subjects at these sites to have skin biopsies collected, and if done, they will need to have provided informed consent to this component. Paired lesional and non-lesional biopsies will be collected at baseline. At the post-baseline visit, 1 biopsy will be collected from the original lesion; no skin biopsy will be collected from non-lesional skin at the post-baseline visit.
- s) Photography will be performed at selected trial sites. It is voluntary for subjects at these sites to have photographs taken, and if done, they will need to have provided informed consent to this component.
- t) Interviews will be conducted at selected trial sites. The interview will be scheduled to occur as soon as possible and within 14 days after Week 14 (Visit 12).

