### 6.2 Administration of IMP

#### General

Dosing visits are shown in the schedule of trial activities (Section 1.3). Dispensing of the IMP will be handled by an IRT system. The IRT system will assign the required kit numbers for each subject at each dispensing visit.

From randomization, LEO 138559 and placebo will be administered SC for a period of 14 weeks (Visits 3-12, with the last IMP administration at Week 14 [Visit 12]) according to 1 of the following treatment regimens:

- Dose regimen 1: LEO 138559 █ mg SC Weeks 0, 1, 2, 3 and then █ mg SC Q2W from Week 4 (50 subjects).
- Dose regimen 2: LEO 138559 █ mg SC Weeks 0, 1, 2 and then █ mg SC Q2W from Week 4 \* (50 subjects).
- Dose regimen 3: LEO 138559 █ mg SC Weeks 0 and 2 and then █ mg SC Q2W from Week 4 \* (50 subjects).
- Dose regimen 4: LEO 138559 █ mg SC Weeks 0 and 2 and then █ mg SC Q2W from Week 4 \* (50 subjects).
- Placebo regimen: Placebo SC Weeks 0, 1, 2, 3 and then placebo SC Q2W from Week 4 \* (50 subjects).

\* In addition to placebo administrations to subjects in the placebo group (at Weeks 0, 1, 2, 3, 4, 6, 8, 10, 12, 14), placebo administrations will also be used to mask the weekly loading doses, and the different dose levels of active IMP.

THIS DOCUMENT CONTAINS CONFIDENTIAL INFORMATION AND MUST NOT BE COPIED OR MADE AVAILABLE TO ANY THIRD PARTY WITHOUT THE PRIOR WRITTEN CONSENT OF THE LEO PHARMA GROUP

The first day of dosing is considered Day 1 (Week 0). Each subject will receive a total of 3 SC injections (2 mL + 2 mL + 1 mL) per dose with either LEO 138559 or placebo, or a combination, to maintain the blinding, and to achieve a total volume of 5 mL per dose as shown in [Panel 6](#).

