### **After IMP administration**

At Weeks 0, 1, 2, 3, and 4, subjects will be monitored for potential immediate drug reactions for a minimum of 2 hours after IMP administration. Vital signs will be taken immediately (within 5 minutes) after last IMP administration, as well as after 30 minutes ( $\pm$  5 minutes), after 1 hour ( $\pm$  5 minutes), and after 2 hours ( $\pm$  5 minutes), or until stable, whichever is later **(for requirements specific for EU countries i.e. CZ, DE, ES, FR, HU, PL and RO, see Section 12.5.1)**. Vital signs will be documented in the eCRF.

As with any Ab, allergic reactions to dose administration are possible. The World Allergy Organization has categorized anaphylaxis into 2 subgroups: allergic anaphylaxis (mediated by an immunologic mechanism) and nonallergic anaphylaxis (which has a nonimmunologic cause) (64). The clinical criteria for defining anaphylaxis for this trial are listed in Appendix 4 (Section 12.4) and (65). Appropriate drugs, such as epinephrine, antihistamines, corticosteroids, etc., and medical equipment to treat acute anaphylactic reactions must be immediately available at trial sites, and trial personnel should be trained to recognize and respond to anaphylaxis according to local guidelines.

If an anaphylactic reaction occurs, a blood sample will be drawn from the subject 1) as soon as possible after the event, 2) at 60 minutes ( $\pm$  30 minutes) after the event, and 3) at discharge for analysis of serum tryptase at the central laboratory.

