### Panel 10: Overview of PROs to be completed

PROs to be completed at home (eDiary)	PROs to be completed at the trial site (electronic device)

To be completed in the morninga)
 
Nocturnal [REDACTED] (Section 8.3.5.2)
 
Difficulty [REDACTED] (Section 8.3.5.3)
 
Frequency of [REDACTED] During the Night (Section 8.3.5.4)
 
To be completed in the eveninga)
 
ADSD (all components) (Section 8.3.5.5)
	
DLQI (Section 8.3.5.6)
 
POEM (Section 8.3.5.7)
 
EQ-5D-5L (Section 8.3.5.8)
 
WPAI-SHP (Section 8.3.5.9)
 
HADS (Section 8.3.5.10)
 
PGI-S (Section 8.3.5.11)
 
[REDACTED]
 
ADSD
 
Nocturnal [REDACTED]
 
Difficulty [REDACTED]
 
Frequency of [REDACTED] During the Night
 
PGI-C (Section 8.3.5.12)
 
[REDACTED]
 
ADSD
 
Nocturnal [REDACTED]
 
Difficulty [REDACTED]
 
Frequency of [REDACTED] During the Night

a) The morning assessments will only be completed until Week 16, the evening assessments will be completed until Week 32.

**Abbreviations:** ADSD = Atopic Dermatitis Symptom Diary; DLQI = Dermatology Life Quality Index; eDiary = electronic diary; EQ-5D-5L = EuroQol 5-Dimension Health Questionnaire 5 Level; HADS = Hospital Anxiety and Depression Scale; PGI-C = Patient Global Impression of Change; PGI-S = Patient Global Impression of Severity; POEM = Patient-Oriented Eczema Measure; PRO = patient-reported outcome; WPAI-SHP = Work Productivity and Activity Impairment: Specific Health Problem.

At the screening visit, the subjects will receive an eDiary device and training in using the device. The subjects must start completing the eDiary at least 1 week prior to baseline, but preferably from the date the subjects receive the eDiary. From Week -1 to Week 16, the subjects will be asked to complete the eDiary twice daily, once in the morning and once in the evening. After Week 16, up to Week 32, the subjects will be asked to complete the eDiary in the evening only (Panel 10).

THIS DOCUMENT CONTAINS CONFIDENTIAL INFORMATION AND MUST NOT BE COPIED OR MADE AVAILABLE TO ANY THIRD PARTY WITHOUT THE PRIOR WRITTEN CONSENT OF THE LEO PHARMA GROUP

Between Week -1 and Week 32, an e-mail notification alarm will inform the investigator/site staff about non-compliance with eDiary completion. In case of non-compliance, the investigator should remind the subject of the importance of completing the eDiary daily.

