### 8.4.1 Vital signs

Vital signs (resting BP, pulse, and body temperature) must be assessed prior to IMP administration according to the schedule of trial activities (Section [1.3](#)). Vital signs will be measured in a supine or sitting position following at least 5 minutes of rest, and will include resting blood pressure, pulse, and body temperature. At an unscheduled visit, it will be at the discretion of the investigator if vital signs should be assessed.

In addition, at Weeks 0, 1, 2, 3, and 4, subjects will be monitored after IMP administration for immediate drug reactions for a minimum of 2 hours with vital signs taken immediately (within 5 minutes) after last IMP administration, after 30 minutes ( $\pm$  5 minutes), after 1 hour ( $\pm$  5 minutes), and after 2 hours ( $\pm$  5 minutes), or until stable, whichever is later (**for requirements specific for EU countries i.e. CZ, DE, ES, FR, HU, PL and RO, see Section [12.5.1](#)**).

If a subject presents with an abnormal vital sign, the measurement of the vital sign can be repeated approximately 15 minutes later to verify the first measurement. Should the repeated measurement result in a normal value, the measurement must be repeated once more. If the third measurement verifies the second normal value, the first measurement should be considered false and the second measurement should be recorded in the eCRF. If the third measurement confirms the first measurement abnormal, the second measurement should be considered false and the first measurement should be recorded in the eCRF. Only the measurement considered true should be recorded in the eCRF, but note that all measured values should be documented in source in these scenarios.

In case of a clinically significant abnormal vital sign at screening and/or baseline, it will be at the discretion of the investigator if the subject should be included in the trial in accordance with exclusion criterion no. [15](#). During the trial, if a subject presents with a clinically significant abnormal vital sign, the investigator must take appropriate action, at their discretion.

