#### **11.3.13.2 Vital signs**

The change in vital signs (resting BP, pulse, and body temperature) from baseline to each relevant visit will be summarized as mean, SD, median, minimum, and maximum values for each treatment group. Shift table for clinically significant abnormal vital signs will be presented.

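### Read literally, the date-based baseline rule in Section 11.3.1 selects a post-injection vital-sign reading as baseline for any dosed subject with recorded post-dose Week 0 readings, which conflicts with Section 8.4.1

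*Combined protocol and SAP*

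**What the plan says.** Section 11.3.1 gives one general rule: "Baseline measurements are defined as the latest available observation at or prior to the date of the first IMP administration, unless otherwise specified". Its cut-off is a date; time of day plays no part.

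For vital signs at dosing visits, footnote o of Panel 2 says: "Vital signs must be assessed prior to IMP administration". Section 8.4.1 adds that "at Weeks 0, 1, 2, 3, and 4, subjects will be monitored after IMP administration for immediate drug reactions for a minimum of 2 hours". Section 6.2 gives the timing: "Vital signs will be taken immediately (within 5 minutes) after last IMP administration, as well as after 30 minutes", then at 1 hour and at 2 hours, with monitoring continued until the subject is stable if that is later. Section 6.2 also has these readings entered in the eCRF. The EU schedule (Panel 18, footnote o) is the same for Week 0.

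For the analysis, Section 11.3.13.2 says: "The change in vital signs (resting BP, pulse, and body temperature) from baseline to each relevant visit will be summarized". It also plans a shift table for clinically significant abnormal vital signs. It says neither which Week 0 set is the baseline nor which set is the visit value at later dosing visits.

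**The concern.** For most assessments a date cut-off does no harm. Section 8.1 puts dosing after every other assessment planned for the visit, so anything measured on Day 1 precedes the first injection. Post-dose monitoring is the exception, since it cannot come before the dose. The readings therefore fall on the first-dose date, are recorded, and are later than the pre-dose set, so the rule prefers them.

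At stake is the reference for the vital-sign safety tables. A baseline meant to describe the untreated subject would instead describe the subject after the first injections. A drug effect still present at that point would be subtracted from every later change. An abnormality that first appeared after dosing and was still there at the last reading would be tabulated as already present at baseline.

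**Working it through.** The plan states no figure to reproduce. The check is a count of readings, followed by an application of the rule.

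**Vital-sign sets on the first-dose date (Day 1, Week 0)**

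- Before injection: 1 set (Panel 2 and Panel 18, footnote o; Section 8.4.1).
- After the last injection: within 5 minutes; at 30 ± 5 minutes; at 1 hour ± 5 minutes; at 2 hours ± 5 minutes = 4 sets (Section 6.2; Section 8.4.1).
- Total: 1 + 4 = 5 scheduled sets, with more possible if the subject is not yet stable.

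**Applying Section 11.3.1**

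- All 5 sets carry the date of first IMP, so all 5 qualify.
- The latest scheduled set is at 120 ± 5 minutes, that is 115 to 125 minutes after the last injection, or later if monitoring is extended.
- Section 11.3.13.2 specifies nothing different, so the exception clause in Section 11.3.1 is not triggered.

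**Setting this beside Section 8.4.1**

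That section leaves inclusion to the investigator's discretion, under exclusion criterion 15, when a vital sign is abnormal and clinically significant at screening or baseline. This decision comes before randomization and dosing. The baseline vital sign it refers to must be pre-dose. The two sections therefore point to different readings.

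**Effect on the change from baseline**

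Let P be a subject's Day 1 pre-dose value, L the last Day 1 reading and V the value at a later visit.

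- Change under the written rule: V − L.
- Change from the pre-dose value: V − P.
- Difference: (V − L) − (V − P) = P − L.

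Every later change for that subject is displaced by the same P − L. The active-minus-placebo contrast in mean change is displaced by mean(P − L) in the active arm minus mean(P − L) in the placebo arm. A shift common to all arms cancels from this contrast but stays in each arm's own mean change.

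**Effect on the shift table**

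The baseline category is that of L, not P.

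- Normal at P, abnormal after dosing, normal again by L: baseline stays normal, so no misclassification.
- Normal at P, still abnormal at L: counted as abnormal at baseline.
- Abnormal at P, normal at L: counted as normal at baseline.

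**With a date-and-time cut-off**

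Only 1 of the 5 sets qualifies, the pre-dose set. If it is missing, the screening value is the fallback. The 4 post-dose sets become on-treatment data.

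**The case against.** The best defence is that a pre-dose baseline is plainly intended. Section 8.4.1 treats the scheduled pre-dose assessment separately from the additional monitoring and uses the baseline value for inclusion. A programmer might pick the pre-dose set by convention, and Section 11.3.1 leaves the SAP to be finalized before unblinding. The point about intention stands, and it means the documents conflict rather than that a post-dose baseline was chosen. It does not remove the problem: the only stated analysis rule gives the other answer, and no text supplied corrects it.

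Three stronger readings are tempting, and the documents do not support them.

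- *Every subject's baseline is a post-injection reading.* This follows only from the literal rule, and only for dosed subjects with at least one recorded post-dose Week 0 reading. Others keep the pre-dose value.
- *Diary baselines are contaminated too.* Because "the subjects will be asked to complete the eDiary twice daily, once in the morning and once in the evening", an evening ADSD entry can fall on Day 1 after dosing. But inclusion criterion 9 defines the baseline weekly average of the Worst item as Day -7 to Day -1, and that item is the only listed ADSD endpoint. The other diary items are morning entries about the night before.
- *First-dose reactions would vanish from the safety assessment.* Section 8.4.1 has any new clinically significant abnormality after screening reported as an AE, and Section 11.3.13.1 defines treatment emergence by the first dose, not by this baseline. A transient change that resolves before the last reading never enters the baseline.

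Nor is there a basis for expecting a large shift. Section 2.2.3 describes slow absorption, with time to maximum concentration measured in days. All arms receive three injections totalling 5 mL (Section 6.2), so effects of the injection procedure should be largely shared with placebo.

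**Conclusion.** The point holds in a limited form. As written, Section 11.3.1 gives the wrong vital-sign baseline for dosed subjects with recorded post-dose Week 0 readings: the 2-hour or later set in place of the pre-dose set that Section 8.4.1 relies on.

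The displacement is P − L per subject. Its size cannot be estimated, because the documents report no vital-sign data; it may be small. It matters to the between-arm comparison only if an effect that differs between active and placebo is still present at the last Day 1 reading.

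The damage is confined to the descriptive change-from-baseline summaries and the shift table, which carry no hypothesis test. The primary endpoint and its testing, the TEAE endpoint, and the ECG, laboratory and diary endpoints are untouched.

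This conclusion assumes that the general rule is applied as worded and that no later SAP text specifies a pre-dose vital-sign baseline.

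**What to change.** - **Section 11.3.1:** define baseline as the latest observation before the date and time of the first IMP injection.
- **Section 11.3.13.2:** name the Week 0 pre-dose set as the vital-sign baseline, and the pre-dose set as the visit value at later dosing visits. Weeks 1 to 4 have the same five sets, and EU sites also take post-dose readings from Week 5 onwards.
- **Section 11.3.13.2:** summarize post-dose sets as change from the same-visit pre-dose value, so that the immediate-reaction monitoring is analyzed for its stated purpose.

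The cost is a few sentences, which can go into the SAP before the randomization code is broken. No new data are needed: Section 6.8.3 already records the date and time of all three injections. The documents do not say whether a clock time is stored with each vital-sign set, but a label separating pre-dose from post-dose sets is enough.

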### **11.3.2 Handling of missing values**

The methods for handling of missing values for the efficacy endpoints are described in Sections [11.3.7](#), [11.3.8](#), and [11.3.9](#).

### **11.3.3 Disposition of subjects**

The reasons for permanent discontinuation of IMP or withdrawal from trial will be presented for all randomized subjects by last visit attended and by treatment group.

### **11.3.4 Demographics and other baseline characteristics**

Descriptive statistics of demographics and other baseline characteristics will be presented for all randomized subjects and by treatment group. Presentations of age, sex, ethnicity, race, and baseline EASI score by treatment group will also be given by baseline disease severity (baseline vIGA-AD score), region (Japan, Other countries), prior use of biologics or systemic JAK inhibitors for AD (Yes/No), and baseline biopsy status (willingness to provide biopsies: Yes/No).

Other baseline characteristics include height, weight, body mass index, duration of AD, concurrent diagnoses (from medical history and indications for concomitant medication), concomitant medication, and previous AD treatments.

THIS DOCUMENT CONTAINS CONFIDENTIAL INFORMATION AND MUST NOT BE COPIED OR MADE AVAILABLE TO ANY THIRD PARTY WITHOUT THE PRIOR WRITTEN CONSENT OF THE LEO PHARMA GROUP

### 11.3.5 Exposure and treatment compliance

Exposure to treatment will be presented for the safety analysis set as days of exposure per treatment group.

The cumulated dose administered to each subject will be determined and summarized descriptively. For subjects who withdraw from the trial, are lost to follow-up, or permanently discontinue IMP, their cumulated dose will be calculated up until the time of withdrawal/permanent discontinuation of IMP/loss to follow-up.

Treatment compliance will be presented for the safety analysis set per treatment group as the percentages of missed IMP doses.

### 11.3.6 Testing strategy

The following hierarchical procedure will be used to ensure strong control of the familywise error rate at the 5% significance level (two-sided significance tests), when testing the null hypotheses associated with the primary endpoint, percent change in EASI score from baseline to Week 16:

1. LEO 138559 [REDACTED] mg SC Weeks 0, 1, 2, 3 and then [REDACTED] mg Q2W from Week 4 (dose regimen 1) versus placebo.
2. LEO 138559 [REDACTED] mg SC Weeks 0, 1, 2 and then [REDACTED] mg Q2W from Week 4 (dose regimen 2) versus placebo.
3. LEO 138559 [REDACTED] mg SC Weeks 0 and 2 and then [REDACTED] mg Q2W from Week 4 (dose regimen 3) versus placebo.
4. LEO 138559 [REDACTED] mg SC Weeks 0 and 2 and then [REDACTED] mg Q2W from Week 4 (dose regimen 4) versus placebo.

Under the hierarchical procedure, the first null hypothesis (the difference in the mean percent change in EASI score from baseline to Week 16 between dose regimen 1 and placebo is equal to 0), is tested at the 5% significance level. If that null hypothesis is rejected, the procedure will proceed to test null hypothesis 2 at the 5% significance level. However, if the first null hypothesis cannot be rejected, the procedure stops and null hypotheses 2-4 will not be formally tested. The procedure continues in this fashion, until it either encounters a null hypothesis that cannot be rejected, or all null hypotheses have been rejected. For the purposes of the hierarchical testing procedure, the hypothesis tests will be based on the analysis of the primary estimand for the primary endpoint.

